## **7.7 Adjustments for Multiplicity**

For comparison of percentage change in TG of three groups with placebo, 100mg vs. 50 mg, and 150mg vs. 100mg, the post hoc tests will be used to detect which group differ from the rest while statistical significance of ANCOVA or Kruskal-Wallis test. For ANCOVA, the required significance criterion alpha is 0.05 divided by the total number of tests. To correct the multiple testing for primary endpoint, the p-value will be adjusted according to Bonferroni's method to reject the null hypothesis (p-value <0.05/m, m= number of tests). In addition, two independent t-test will also be used for pairwise comparison (p-value=0.05 for all multiple tests). For Kruskal-Wallis test, two independent t-test or Wilcoxon rank-sum test will be used for pairwise comparison (p-value=0.05 for all multiple tests).

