- The ITT population includes all randomized patients who meet all inclusion criteria and exclusion criteria, take at least one study medication and have at least one post-baseline measurement
- The PP population is a subset of the ITT population and includes all randomized patients who complete 12 weeks of treatment without major protocol violation.
- All subjects who received at least one study medication will be included in the safety analysis population.
- Primary efficacy analysis will be performed in ITT and PP population, secondary efficacy analyses will be performed in ITT population and safety analyses will be performed using safety population.
- Last observation carried forward (LOCF) will be used to approach the missing data of primary endpoint in ITT population. No missing data will be imputed for the secondary efficacy or safety analyses.
- Descriptive statistics will be summarized as n, mean, standard deviation, median and range for continuous parameters, and will be tabulated as frequency and percentage for categorical parameters.
- To compare TG percentage change from baseline to week 12 between 3 treatment groups, the ANOVA with

Bonferroni adjustment will be performed, or if assumption of normality is not met, then Kruskal-Wallis Test will be performed. If the differences in baseline characteristics, such as gender, age, weight etc., are observed, the ANCOVA will adjust for the significant variables in the primary analysis. The within-group change from baseline in each treatment group will be assessed using the paired-T test. If the normal assumption is violated, Wilcoxon signed-rank test will replace the paired-T test.

- Other continuous variable at each visit and change at post-baseline visits will be summarized by descriptive statistics and be analyzed by means of ANOVA with Bonferroni adjustment. Paired T-Test will be used to compare the change from baseline within treatment groups. If the normal assumption is violated, non-parametric statistical methods such as Kruskal-Wallis Test or Wilcoxon Signed-Rank Test will be used.
- Categorical variables will be tabulated with related frequency and percentages and be compared by using Chi-square or Fisher's exact test.

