## **9 STATISTICAL METHODS**

### **9.1 Primary Hypothesis**

The primary endpoint in a study is the percentage change from baseline of TG by Antroquinonol compared to placebo after 12 weeks. The primary hypothesis of the study is that:

$H_0$ : the percentage change of TG score in four groups are equal versus

$H_A$ : at least one of the percentage change of TG score in four groups is different

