## 9.3 Primary Endpoint Analysis

The primary efficacy endpoint (percentage change of TG) for assessing the superiority of Antroquinonol (50mg, 100mg, 150mg) to placebo is the percentage change in patients with hyperlipidemia by using analysis of covariance (ANCOVA) model using baseline measurement as covariates (model 1). If the differences in baseline characteristics, such as gender, age, weight etc., are observed, for comparing the effectiveness between the treatment groups and placebo, the model will be performed by multiple linear model (model 2) to adjust characteristics.

Model 1:  $Y_{\text{percentage change of TG} (\%)} = \beta_1 + \beta_2 X_{\text{treatment}} + \beta_3 X_{\text{baseline of TG}}$

Model 2:  $Y_{\text{percentage change of TG} (\%)} = \beta_1 + \beta_2 X_{\text{treatment}} + \beta_3 X_{\text{baseline of TG}} + \beta_4 X_{\text{significant characteristic in baseline}}$

If statistical significance of ANCOVA treatment effect is reached ( $p\text{-value} < 0.05$ ), Bonferroni's method, and two independent t-test (section 7.7) will be performed post hoc analysis for pairwise comparison of percentage change in TG (Antroquinonol 50 mg vs. Placebo, Antroquinonol 100 mg vs. Placebo, Antroquinonol 150 mg vs. Placebo, Antroquinonol 100 mg vs. Antroquinonol 50 mg and Antroquinonol 150 mg vs. Antroquinonol 100 mg).

If the normal assumption is violated for percentage change of TG in any treatments, Kruskal-Wallis test will replace ANCOVA. If statistical significance of Kruskal-Wallis test treatment effect is reached ( $p\text{-value} < 0.05$ ), two independent t-test or Wilcoxon rank-sum test will be performed post hoc analysis for pairwise comparison of percentage change in TG (Antroquinonol 50 mg vs. Placebo, Antroquinonol 100 mg vs. Placebo, Antroquinonol 150 mg vs. Placebo, Antroquinonol 100 mg vs. Antroquinonol 50 mg and Antroquinonol 150 mg vs. Antroquinonol 100 mg).

Protocol: GHLIP-2-001

Study Sponsor: Golden Biotechnology Corporation

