## 9.7 Interpretation and Conclusion

All tests are two-tailed unless otherwise specified and the overall significant level is set to be 0.05. When the number of hypothesis in a test is increased, the Bonferroni correction would be used to test each of the individual tests at a significance level of  $0.05/m$  ( $m$ = number of tests=5, section 9.3). Statistical significance will be demonstrated if the p-value is less than the significance level of test. Regardless of the outcome declared statistically significant, all results could be stated on the Clinical Study Report (CSR).

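### The SAP sets 0.05/5 for the five primary TG pairs, but section 7.7 names only an unadjusted 0.05 after Kruskal-Wallis and adds unlabelled 0.05 t-tests after ANCOVA

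*SAP*

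**What the plan says.** **SAP 9.7** gives the general rule: "All tests are two-tailed unless otherwise specified and the overall significant level is set to be 0.05". For several hypotheses, "the Bonferroni correction would be used to test each of the individual tests at a significance level of" 0.05/m, with m = 5 and a pointer to section 9.3. Significance is then declared when p falls below the level of the test concerned.

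**SAP 9.3** lists the same five pairs in both branches: 50, 100 and 150 mg each against placebo, 100 against 50 mg, and 150 against 100 mg. They are tested only if the omnibus test gives p < 0.05.
- After ANCOVA: "Bonferroni's method, and two independent t-test (section 7.7) will be performed post hoc analysis for pairwise comparison of percentage change in TG".
- After Kruskal-Wallis, used when normality fails in any arm: "two independent t-test or Wilcoxon rank-sum test will be performed post hoc analysis for pairwise comparison of percentage change in TG".

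**SAP 7.7** supplies the levels. After ANCOVA, 0.05 divided by the number of tests is the criterion to be met, and then: "In addition, two independent t-test will also be used for pairwise comparison (p-value=0.05 for all multiple tests"). For the other branch: "For Kruskal-Wallis test, two independent t-test or Wilcoxon rank-sum test will be used for pairwise comparison (p-value=0.05 for all multiple tests").

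**SAP 9.1** states the primary alternative as "at least one of the percentage change of TG score in four groups is different".

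**SAP 9.2** gives a general two-group rule: Student's t-test, or Wilcoxon rank-sum if normality is not met.

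**The Protocol Summary** (Statistical Methodology) attaches the correction to ANOVA only: "Bonferroni adjustment will be performed, or if assumption of normality is not met, then Kruskal-Wallis Test will be performed". Neither there nor in Protocol 9.4 is a pairwise test named after Kruskal-Wallis. **SAP 12** reports no change to the protocol.

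**The concern.** A pair with p between 0.01 and 0.05 passes one written rule and fails another. After Kruskal-Wallis this is a plain conflict between 7.7 and 9.7. After ANCOVA it is a missing label: two sets of tests on the same pairs, at two levels, with no statement that one set is only supportive. The decision sentence in 9.7 refers to the level of whichever test is meant, so it does not rank them.

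At stake is which doses are reported as better than placebo, or as different from the next dose, on the primary endpoint. If the 0.05 results are read as confirmatory, the overall 0.05 in SAP 9.7 is not kept in several plausible dose-response patterns.

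**Working it through.** **Inputs.** 24 evaluable per arm, effect 27.5 and SD 40 (Protocol 9.2); five pairs and the 0.05 gate (SAP 9.3); m = 5 (SAP 9.7). Assumed: normal data, equal SDs, no covariate.

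**The plan's own figure.** 0.05/5 = 0.01 per pair. This reproduces.

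**Without a gate.** Five independent tests at 0.05 would give 1 − 0.95⁵ = 22.6%. Simulated with the shared arms, the figure is 18.2%. Neither applies here, because the pairs are tested only after a significant omnibus test.

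**With the gate.** Simulate four arms of 24, require F significant at 0.05, then run pooled t-tests on the five pairs. With 200,000 trials per pattern, the simulation error is below 0.1 percentage point. *Any false claim* counts every truly null pair in either direction. *False superiority* counts only an inactive dose declared better than placebo.

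| Active doses (effect 27.5) | Null pairs | Any false claim, 0.05 | at 0.01 | False superiority, 0.05 | at 0.01 |
|---|---|---|---|---|---|
| none | 5 | 4.9% | 3.3% | about 2% | about 1% |
| only 50 or only 150 mg | 3 | about 11% | 2.7% | 4.2% | 0.9% |
| only 100 mg | 2 | 8.4% | 1.8% | 4.2% | 0.9% |
| 100 and 150 mg | 2 | 9.5% | 2.0% | 2.5% | 0.5% |
| all three | 2 | 8.4% | 1.9% | 0% | 0% |
| 50 and 150 mg | 1 | 4.8% | 1.0% | 2.5% | 0.5% |

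With all three doses equally active, every false claim is dose-versus-dose.

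**Effect size.** With only 150 mg active, any false claim at 0.05 is 4.2% at effect 5, 5.5% at 10, 9.3% at 20 and 12.2% at 50. At effect 50 the gate passes in over 99% of trials, so the rate has levelled off.

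**Kruskal-Wallis branch.** Using the Kruskal-Wallis gate and Wilcoxon pairs at 0.05 on the same normal data (100,000 trials), any false claim is 4.7% with all arms equal, 10.7% with only 150 mg active and 8.0% with all three active. At 0.01 the last two are 2.5% and 1.8%. With an assumed log-normal outcome (skewness 1.26), they are 10.9–11.5% and 8.5–8.6% at 0.05. The pattern is the same.

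**How often the level changes a verdict.** Among trials passing the gate at effect 27.5, this is the share in which the superiority verdict for at least one dose differs between 0.01 and 0.05:

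| SD | One active dose | Two | Three |
|---|---|---|---|
| 40 (Protocol 9.2) | 30% | 48% | 57% |
| 20 (assumed, intermediate) | about 5–6% | about 5–6% | about 5–6% |
| 5.3 (larger SD in SAP 5) | 4% | 2% | 0% |

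**Power per comparison.** The noncentrality is 27.5 / (40 × √(2/24)) = 27.5/11.55 = 2.38, with 46 degrees of freedom. The two-sided critical values are 2.013 at 0.05 and 2.687 at 0.01, giving power 0.64 and 0.39.

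**The case against.** The strongest defence has four parts.

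- **Bonferroni already decides after ANCOVA.** SAP 7.7 makes 0.05/m the level for rejecting the null, the t-tests come afterwards as an addition, 9.7 repeats 0.05/5, and the protocol pairs ANOVA with Bonferroni. This largely stands. A reader might infer that the SAP gives no guidance on which result counts, but after ANCOVA that goes too far. What is missing is a label on the extra tests. The defence does not reach the Kruskal-Wallis branch, where 7.7 gives no corrected level.

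- **The omnibus gate protects the trial.** It protects the hypothesis in SAP 9.1, at about 5%. A reader might infer that the primary hypothesis test itself is inflated, or that the familywise error is 18 to 23%. The documents support neither, because 9.3 imposes the gate. But the gate does not cover the remaining null pairs once one arm differs enough to open it.

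- **The choice between t-test and Wilcoxon is not free.** SAP 9.2 has a two-group rule. Kruskal-Wallis is triggered by non-normality in any arm, so 9.3 may mean that 9.2 is applied pair by pair. This stands as a possible reading, and error rates that assume the better of two p-values may be picked are not supported. What remains is that 7.7 and 9.3 do not invoke 9.2 at that point, and no normality criterion is named anywhere.

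- **This is phase II and the pairwise tests are called post hoc.** True, and it lowers the severity. But 9.7 itself chose an overall 0.05, and 9.3 frames the analysis as superiority over placebo.

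**Conclusion.** The point holds in limited form. After Kruskal-Wallis, SAP 7.7 contradicts 9.7. After ANCOVA, the SAP leans to Bonferroni but leaves the parallel 0.05 tests unlabelled.

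Read as confirmatory, the 0.05 tests give about 8 to 11% false pairwise claims at the planning effect when two or three pairs are null. The rate is about 5% or less with one null pair, with all arms equal or with very small effects. A reader might take the 8 to 11% as the chance of wrongly declaring a dose better than placebo. It is not: it includes dose-versus-dose errors and errors in the harmful direction. False superiority over placebo is about 4.2%, 2.5% and 0% with one, two and three active doses.

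The verdict changes of 30 to 57% depend on SD 40 and shrink to a few per cent at smaller SDs. The documents give both SD 40 and much smaller values, so the full range should be kept in view. How often the Kruskal-Wallis branch would be entered cannot be derived.

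This should be fixed, but it is not disqualifying: the stated primary hypothesis is the omnibus null, which is held at about 5%, and the direct contradiction is confined to one branch.

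**What to change.** Before unblinding, amend the SAP wording:

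1. In 7.7, 9.3 and 9.7, state that 0.05/5, as 9.7 already says, decides the five TG pairs in both branches.
2. Delete the unadjusted 0.05 tests or label them descriptive.
3. In 7.7, say which pairwise test follows Kruskal-Wallis: Wilcoxon rank-sum throughout, or the SAP 9.2 rule with a named normality criterion.
4. In SAP 12, list as additions to the protocol both the extra t-tests after ANCOVA (if kept) and the pairwise tests after Kruskal-Wallis.

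No data, arm or primary test changes. The cost is that some nominally significant pairs can no longer be claimed: power per comparison at difference 27.5, SD 40 and 24 per arm is 0.39 at 0.01, against 0.64 at an unadjusted 0.05.

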## **7.8 Multi-center Studies**

Total efficacy-evaluable patients will be enrolled from multiple study sites, i.e., National Taiwan University Hospital, China Medical University Hospital, National Cheng Kung University

**Protocol: GHLIP-2-001**

**Study Sponsor: Golden Biotechnology Corporation**

Hospital, Far Eastern Memorial Hospital, Taipei Veterans General Hospital, and Chang Gung Memorial Hospital, Linkou branch. With the intention of pooling the data for analysis, all the investigators from participating institutions will follow the study protocol and conduct the clinical trial to improve the consistency across centers. All collected clinical data will be managed, centralized and summarized with respect to demographic characteristics, and efficacy and safety observations.

## **7.9 Data Management System and Analysis Software**

The data collected will be entered into the study database against the paper CRF and stored in the Clinical Data Management Systems (CDMS). The data backup is exhibited by data management personnel. The data will be exported to Statistical Analysis System® (SAS) for Windows (Version 9.4, SAS Institute, Cary, North Carolina, USA) to generate the subject listings, tabulations, and statistical analyses.

## **7.10 Coding Dictionary**

In order to create a standard language that is comparable across all therapeutic teams and provide standardization for statistical analysis, adverse events recorded on the paper CRF will be coded by medical dictionaries/thesaurus. In this study, the Medical Dictionary for Regulatory Activities (MedDRA) version 20.0 will be used to map adverse events verbatim to Preferred Terms (PT) and System Organ Class (SOC).

## **7.11 Data Handling and Transfer**

All collected clinical data or external data will be managed centralized and stored in the clinical data management systems. The system of variable coding will follow rules of Bestat Pharmaservices Corp.

Protocol: GHLIP-2-001

Study Sponsor: Golden Biotechnology Corporation

## 7.12 Programming Specifications

The summary statistics for continuous variables will be entitled as Number, Mean±SD, Median, Range and 95% C.I. in the table, which represent the number of observations, mean value plus/minus standard deviation, median value of observations, minimum and maximum, lower bound and upper bound of the 95% confidence interval. Range and 95% C.I. are given in parentheses.

Unless otherwise noted, the summary statistics for continuous variables will be printed out to one decimal place except for the standard deviation and confidence interval. The standard deviation and confidence interval will be expressed to 2 decimal places.

In analysis of categorical variable, descriptive statistics will be entitled as frequencies and percentages. All table percentages will be reported with two decimal points unless otherwise specified.

All statistical tests will be conducted under a two-tailed, significance level of 0.05 with related p-value. The p-value will be reported to three decimal places. An asterisk indicates the statistical significance. P-value less than 0.001 will be reported as "< 0.001\*" and p-value greater than 0.999 will be expressed as "> 0.999".

## 8 SUMMARY OF STUDY DATA

Continuous variables will be summarized by descriptive statistics: number of observations, mean, median, standard deviation, range and 95% C.I. Frequency counts and percentages (based on non-missing sample size) of observed levels will be reported for categorical variables.

Protocol: GHLIP-2-001

Study Sponsor: Golden Biotechnology Corporation

## 8.1 Disposition of Subject and Withdraws

Participants who signed the informed consent form will follow study-related procedures described in the protocol till the end of study. However, subjects are free to withdraw from the study at any time. The number of screened, randomized, reached study completion will be counted and summarized. The reason causing the discontinuation will be provided as listing report as well. The allocation in each treatment group will be specified and the size of analysis populations will be determined by treatment.

## 8.2 Protocol Violation and Deviations

Protocol deviations includes but do not restrict to the following:

- Out of visit and procedure window.
- Deviations from the expected dispensing regimen.
- Intentional deviation from the protocol, GCP or regulations by study personnel in a non-emergency setting.

Protocol violations includes the following:

- Violate the eligibility founded after the randomization.
- Failure to obtain valid informed consent.

## 8.3 Demographics

The following demographic and baseline characteristics will be ascertained at the time of study recruitment: gender, age, height, weight, BMI, pregnancy status (females only), medical history, physical examination, and concomitant medications. Continuous data will be summarized by descriptive statistics using number of specific item, mean, median, standard deviation,

**Protocol: GHLIP-2-001**

**Study Sponsor: Golden Biotechnology Corporation**

maximum and minimum. Frequencies and percentages are tabulated for categorical data. The analysis of baseline characteristics will be performed using safety population. If the differences in baseline characteristics are observed, the multiple linear model will adjust for the significant variables in the primary analysis. The baseline demographic characteristics will be compared using Chi-square test or Fisher's exact test for categorical variables and t-test or Wilcoxon Rank-Sum test for continuous variables.

## **8.4 Baseline and Screening Conditions**

### **8.4.1 Baseline Medical History**

No coding or analysis items for medical history of subjects will be planned. The listing report will present the raw medical history record of subjects.

### **8.4.2 Baseline Physical Exam**

Results of baseline physical examination for abnormality will be listed.

## **8.5 Prior and Concurrent Medications**

Data coding for Adverse Events will be based on pre-existing/concurrent conditions or treatments. All prior and concurrent data will be presented by patients and by treatment in the listing report.

## **8.6 Treatment Compliance**

Patients will be instructed to take a total of three capsules of Antroquinonol and/or placebo in different combination once per day and return to the study site on the next visit. A record of the

**Protocol: GHLIP-2-001**

**Study Sponsor: Golden Biotechnology Corporation**

number of capsules dispensed, taken and returned for each patient must be documented on the CRF. Compliance will be assessed from the information recorded in the CRF, including study medication count, start and end date of therapy. The treatment compliance rate will be determined by the number of taken drugs divided by number of taken drugs divided by number of days of treatment taken  $\times$  3 capsules per day that should be taken and presented in the percentage format, given by:

- Treatment Compliance (%) =  $\frac{\text{Quantity of total dispensed} - \text{Quantity of total returned}}{\text{Treatment period (84 days)}} \times 100\%$

## **9 STATISTICAL METHODS**

### **9.1 Primary Hypothesis**

The primary endpoint in a study is the percentage change from baseline of TG by Antroquinonol compared to placebo after 12 weeks. The primary hypothesis of the study is that:

$H_0$ : the percentage change of TG score in four groups are equal versus

$H_A$ : at least one of the percentage change of TG score in four groups is different

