9.2. Sample Size Considerations

The primary efficacy endpoint in this trial is “to compare the percentage change of triglyceride (TG) from baseline following a 12-week regimen of Antroquinonol versus placebo.” The objective of this trial is to assess the efficacy of the study treatment compared with control treatment. According to the literature review (FDA statistical reviews of Fibrate), the TG reduction percentage change of Fibrate from baseline to last visit was 36.6% for subjects who were treated with the study treatment, and 0.7% increased for the control treatment. According to prior published clinical reference, it is assumed that the mean TG percentage reduction is 27.5% and standard deviation is 40. The evaluable patient number should be at least 24 patients for each group under one-sided significance level 0.025 and power 90%. Considering a 20% drop-out rate, a sample size of 30 patients should be enrolled to each group, and a total of 120 patients will be recruited into this study. The sample size calculation was derived using PASS 2008.

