## **5 SAMPLE SIZE DETERMINATION**

The sample size estimation of this study is using two-sample T-test under one-sided significance level 0.025, power 90%. Based on the Davidson's study, the TG reduction percentage change of 130 mg Fenoribrate from baseline to last visit was 36.6% for subjects who were treated with the study treatment, and the standard deviation was 2.4% and 5.3% for the study treatment and the control treatment. Assuming a drop-out rate of 20%, a sample size of 120 patients (30 patients per arm) were required to provide 96 evaluable patients (24 patients for each group) which indicates an achievement of 80% completion rate.

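### The primary test is a four-group equality test that gates the placebo comparisons; it does not express superiority to placebo, the rules after it conflict, and the stated 90% power belongs to none of the steps

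*SAP*

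**What the plan says.** The primary objective (SAP 3.1.1; Protocol 2) and the hypothesis in Protocol 1.2 are directional: TG falls more on Antroquinonol than on placebo. SAP 9.3 opens with the same superiority aim.

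SAP 9.1 nevertheless takes equality of the four groups as the null, against the alternative "at least one of the percentage change of TG score in four groups is different". SAP 9.3 then opens the pairwise comparisons conditionally: "If statistical significance of ANCOVA treatment effect is reached". The Kruskal-Wallis branch has the same condition. Five comparisons follow: each dose versus placebo, 100 versus 50 mg, and 150 versus 100 mg. SAP 9.7 fixes the Bonferroni divisor ("number of tests=5, section 9.3"), so each test is at 0.05/5 = 0.01. SAP 7.7 and 9.3 add independent t-tests on the same five comparisons, and 7.7 puts these at 0.05 each. For the Kruskal-Wallis branch, 7.7 gives only the 0.05 rule.

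The size comes from a different test. Protocol 9.2 gives the inputs: "it is assumed that the mean TG percentage reduction is 27.5% and standard deviation is 40". From these it derives a minimum of 24 evaluable subjects per arm, with 90% power claimed at a one-sided level of 0.025. The method is named in SAP 5: "using two-sample T-test under one-sided significance level 0.025, power 90" per cent. No power is stated for the four-group test, and no dose-response pattern is assumed. Protocol 9.4 describes no gate, although SAP 12 reports no change from the protocol.

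**The concern.** The formal primary hypothesis and the question asked are different. A non-directional test with 3 degrees of freedom can reject because one dose differs from another, or because a dose raises TG. Neither supports the claim.

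The decision rule after the gate is also open. One comparison can fail at 0.01 and pass at 0.05, and the SAP does not say which result counts. Two of the five tests lie outside the placebo objective but use two fifths of the alpha on the Bonferroni route.

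Finally, a reader will take 90% as the chance that the planned analysis finds a 27.5-point effect. At stake are what a positive primary result would mean, control of the error rate, and an honest statement of power.

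**Working it through.** **Inputs.** Difference 27.5 points, SD 40, 24 evaluable per arm, one-sided 0.025 (Protocol 9.2); two-sample t-test (SAP 5); omnibus level 0.05 (SAP 9.3); m = 5 (SAP 9.7). Assumptions: 27.5 is the difference from placebo; the baseline covariate brings no gain in precision; the dose patterns are mine, because the documents give none.

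**1. The plan's own figure.** Standard error = 40 × √(2/24) = 11.55, and 27.5/11.55 = 2.38. Power = Φ(2.38 − 1.96) = 66% by the normal approximation, 64.5% by the noncentral t. The size for 90% is n = 2 × (1.960 + 1.282)² × (40/27.5)² = 44.5, so 45 per arm (46 by t). The stated 24 does not reproduce. It comes close on two other readings: a one-sample formula (25 by t; 89.7% power at 24), or a difference of 36.6 + 0.7 = 37.3 points from the fibrate figures in Protocol 9.2 (26 by t; 88.5% power at 24). The dropout step is right: 24/0.8 = 30.

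**2. The omnibus test.** Noncentral F with 3 and 92 df, λ = 24 × Σ(μᵢ − μ̄)²/40², largest difference from placebo 27.5 in every row:

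| Pattern | Σ(μᵢ − μ̄)² | λ | Power |
|---|---|---|---|
| Mid-point (0, 13.75, 13.75, 27.5) | 378.1 | 5.67 | 47.5% |
| Linear (0, 9.17, 18.33, 27.5) | 420.1 | 6.30 | 52.1% |
| One dose active, or all three equally | 567.2 | 8.51 | 66.3% |
| Two active, one inactive | 756.3 | 11.34 | 79.9% |

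λ uses squared deviations, so a dose that raises TG by 27.5 points rejects the null as often (66%) as one that lowers it by 27.5.

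**3. The gate with 0.01 tests, against Dunnett without a gate.** Simulation, 200,000 trials per pattern, pooled error, two-sided Dunnett critical value 2.39:

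| Pattern | 150 mg, gate + 0.01 | 150 mg, Dunnett | Any dose, gate + 0.01 | Any dose, Dunnett |
|---|---|---|---|---|
| All three active | 40% | 50% | 63% | 75% |
| Only 150 mg active | 40% | 50% | 40% | 50% |
| Two active | 40% | 50% | 56% | 66–67% |
| Linear | 39% | 50% | 43% | 55% |
| Mid-point | 38–39% | 50% | 41% | 54% |

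**4. Where the 10 points come from.** With 0.01 tests and no gate, 150 mg versus placebo has 40.6%. The gate lowers this to between 38% and 40%, a cost of about 1 to 2 points. For any dose, the gate takes 65.1% to 63.1% (all active), 40.6% to 40.0% (one) and 45.1% to 43.4% (linear). The rest comes from testing three comparisons with Dunnett and not five with Bonferroni. For a two-sample t-test, going from 0.05/5 to 0.05/3 alone raises power from 39.0% to 46.6%.

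**5. The unadjusted route.** Gate plus t-tests at 0.05 gives about 55% for 150 mg versus placebo when one dose or all doses are active, but without family-wise control. If one dose is strongly active the gate is practically always open. Two inactive doses are then each tested at 0.05. Independent tests would give 1 − 0.95² = 9.75%; with the shared placebo arm, simulation gives about 9%.

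**6. At 37.3 points.** Omnibus power is 76% to 98%, gate plus 0.01 about 70% to 72% for 150 mg versus placebo, and Dunnett about 80%.

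**The case against.** An omnibus test followed by Bonferroni contrasts is a conventional procedure that controls error, and the contrasts name each dose against placebo. Superiority would be read from them, so the mismatch in SAP 9.1 is partly repaired downstream. That stands for the Bonferroni route. It does not stand for the parallel 0.05 tests or for SAP 7.7's Kruskal-Wallis branch, and the stated primary hypothesis remains one whose rejection does not answer the objective.

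Three stronger readings are tempting, and the documents do not support them:

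- A reader might infer that the omnibus test is why 90% is missed. But the 90% is stated for a two-sample t-test, which itself has only about 65%. With one dose or all doses active the omnibus test is no weaker, and with two active it is stronger.
- A reader might infer that the gate loses many true effects. Under the 0.01 rule it costs 1 to 2 points. It bites harder on an unadjusted 0.05 test: 150 mg passes but the gate fails in 4% to 19% of trials, depending on pattern.
- A reader might infer that Dunnett's gain costs nothing. It is bought by giving up two prespecified dose-versus-dose tests, a real choice about what a phase II trial should learn.

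Precision may also be better than assumed. With a baseline-to-outcome correlation of 0.5 (an assumption), omnibus power would be 61% to 91%. The documents state no correlation.

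**Conclusion.** The point holds on structure. The primary null does not express superiority to placebo, the placebo comparisons depend on rejecting it, and two incompatible rules follow, one of which allows about 9% family-wise error across two inactive doses when the third is strongly active.

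On power, no step has 90% at 24 per arm, 27.5 points and SD 40 without covariate gain: about 65% for the sizing t-test, 47% to 80% for the omnibus test, and 38% to 41% for 150 mg versus placebo through the gate at 0.01. The sizing error is the main cause of the gap and a separate fault. The choice of analysis then accounts for about 10 points per dose, nearly all from the number and type of adjusted tests. The omnibus range rests on assumed dose patterns, and every power figure rises if 37.3 points was meant or if baseline TG predicts the outcome well. The mismatch and the conflicting rules depend on none of these assumptions.

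**What to change.** Amend the SAP before it is approved for database lock and unblinding (SAP 6.2):

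1. Replace the hypothesis in 9.1 by three primary hypotheses, each dose versus placebo.
2. Test them as contrasts from the ANCOVA in 9.3 with Dunnett's adjustment at two-sided overall 0.05, without an omnibus gate.
3. Delete the unadjusted 0.05 t-tests in 7.7 and 9.3 as a decision rule. On the non-parametric branch, drop the gate as well and apply a matching multiplicity adjustment to the three placebo comparisons.
4. Report 100 versus 50 mg and 150 versus 100 mg descriptively, with confidence intervals, and correct m = 5 in 9.7.
5. Restate power for this analysis: about 50% for each dose with a true effect of 27.5 points at SD 40 and 24 per arm, or about 80% if 37.3 points was intended. Say which effect was meant.
6. Record the change in SAP 12.

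This needs no extra patients, visits or data. The cost is the loss of formal dose-versus-dose tests and a less favourable stated power. It does not restore 90%: at 27.5 points even Bonferroni over the three placebo comparisons would need about 59 per arm, which belongs with the sample-size correction.
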